10.2 Recording and Reporting AEs and SAEs in the UK

AEs will be graded according to the CTCAE (Common Terminology Criteria for Adverse Events). The grading must be documented in the patient's medical notes.

Please see diagram in Appendix 1 Safety Reporting Diagrams for further guidance.

All AEs occurring from the point of consent to the end of trial participation must be recorded in the trial MACRO database eCRF as well as in the participant's medical notes.

All SAEs occurring from the point of consent to the end of trial participation must be reported to NCTU on the MCDS-Therapy SAE form via secure e-mail to [contact] or via secure transfer methods and also recorded on the trial MACRO database eCRF.

All SARs occurring from the first participant's dose of IMP to the last participant's end of follow-up must be reported to NCTU on the MCDS-Therapy SAE form and also recorded on the trial MACRO database eCRF.

Following this defined active monitoring period for SARs, investigators are still required to report any SARs or SUSARs they become aware of.

All UK SAEs/SARs must be reported to NCTU using the MCDS-Therapy SAE Form via secure e-mail to [contact] or via secure transfer methods within 24 hours of research staff becoming aware of the event. This will ensure that all the relevant individuals (CI, NCTU trial management and QA management staff and UK Sponsor) are informed of the event in a timely manner.

Preliminary reporting to NCTU via email or telephone is acceptable in order to meet the 24-hour reporting timeline, where circumstances do not allow for immediate completion of the SAE form. However, the SAE form should be completed and submitted as soon as possible after the initial notification in order to comply with reporting timelines.

For each SAE the following information will be collected:

- Full details in medical terms and case description
- Event duration (start and end dates, if applicable)
- Action taken
- Outcome
- Seriousness criteria
- Causality in the opinion of the investigator
- Whether the event is considered expected or unexpected in accordance with the approved RSI if a causal relationship is suspected

Any change of condition or other follow-up information should be submitted to the NCTU via secure e-mail to [contact] or via secure transfer methods as soon as it is available or at the latest within 24 hours of the information becoming available. Events will be followed up until the event is resolved or a final outcome has been reached.

10.3 Recording and Reporting SUSARs

All UK SUSARs occurring from first administration of IMP until the end of the trial must be reported to NCTU as soon as the research site become aware. NCTU will inform the trial UK Sponsor of all SUSARs within 24 hours of becoming aware of the event to ensure timely reporting to the MHRA and REC can be conducted. In the UK, the UK trial Sponsor is responsible for reporting SUSARs to the MHRA and REC.

For international sites the country specific Sponsors will be responsible for reporting SUSARs to their relevant competent authorities and ethics review organisations within each participating country, as per local requirements.

The assessment of expectedness will be performed by the trial CI with input from country specific Sponsor and the site PI^a against the approved Reference Safety Information (RSI) for the trial. The RSI is contained within section 4.8 of the SmPC (PI^b for Australia) for each of the Tegretol[®] 100mg, 200mg and 400mg tablets and Tegretol[®] 100mg/5ml liquid.

Fatal and life-threatening SUSARS in the UK must be reported to the MHRA no later than 7 calendar days after the UK Sponsor has first knowledge of the event. Any relevant follow-up information must be sought and reported within a further 8 calendar days.

Non-fatal SUSARs in the UK must be reported to the MHRA no later than 15 calendar days after the UK Sponsor has first knowledge of the event. Any relevant follow-up information should be sought and reported as soon as possible after the initial report. For international sites the country specific Sponsor will also ensure that safety reporting timelines for competent authorities of participating countries outside of the UK will be adhered to following local requirements.

For UK SUSARs, as soon as a site suspects that a SAR may be a SUSAR they must contact the CI, sponsor representative and the trial manager immediately. Information should be submitted to the NCTU via secure e-mail to [contact] or via secure transfer methods (see Appendix 1 for details). The reporting timeframe starts at day 0 when the Sponsor is in receipt of a minimum set of information:

- Sponsor trial reference and trial name (sponsor reference)
- EudraCT number
- Patient trial number and date of birth
- Name of IMP(s)
- Date of notification of the event
- Medical description of the event
- Date and time of the onset of the event (including event end date if applicable)
- Causality assessment
- Seriousness of the event, particularly if life threatening or fatal
- An identifiable reporter (e.g., Principal Investigator)

This information must be provided on the MCDS-Therapy SAE Form. The UK site is expected to fully cooperate with the NCTU and UK Sponsor in order that a full and detailed report can be submitted to the MHRA and REC within the required timelines. For international sites, the country specific Sponsor will also ensure that safety reporting submissions to competent authorities of participating countries outside of the UK will be adhered to following local requirements.

The Trial Manager will ensure all trial PI^as will be informed of any SUSARs that occur in relation to the trial IMP.

10.4 Responsibilities

10.4.1 Principal Investigator

- Checking for AEs and ARs when participants attend for treatment or follow-up
- Using medical judgement in assigning seriousness and causality and providing an opinion on expectedness of events using the Reference Safety Information approved for the trial
- Ensuring that all SAEs and SARs, including SUSARs, are recorded and reported to the Sponsor within 24 hours of becoming aware of the event and provide further follow-up information as soon as available
- Ensuring that AEs and ARs are recorded and reported to the Sponsor in line with the requirements of the protocol
- Ensuring all AEs are recorded in the eCRF within the trial MACRO database

10.4.2 Chief Investigator

- Clinical oversight of the safety of trial participants, including an ongoing review of the risk/benefit
- Using medical judgement in assigning seriousness, causality and expectedness of SAEs where it has not been possible to obtain local medical assessment
- Using medical judgement in assigning expectedness to SARs in line with the RSI
- Immediate review of all SUSARs
- Review of specific SAEs and SARs in accordance with the trial risk assessment and protocol
- Review/assignment of Medical Dictionary for Regulatory Activities (MedDRA) or body system coding for all SAEs and SARs

- Preparing the clinical sections and final sign off of the DSUR
- Reviewing RSI at least annually and the notification of PI^as of any required updates (may be delegated to NCTU)

10.4.3 UK Sponsor

- Data collection and verification of AEs, ARs, SAEs, SARs and SUSARs onto a database (may be delegated to NCTU)
- Reporting safety information to the independent oversight committees for the ongoing assessment of the risk/benefit ratio throughout the life of the trial (may be delegated to NCTU)
- Assessment of expectedness of any SUSARs (may be delegated to the CI)
- Expedited reporting of SUSARs to the relevant CA and REC within required timelines
- Notification of all investigator sites of any SUSAR that occurs (may be delegated to NCTU)
- Reviewing RSI at least annually and the notification of Pl^as of any required updates (may be delegated to NCTU and CI)
- Preparing tables and other relevant information for the DSUR in collaboration with the CI and ensuring timely submission to all appropriate CAs (including MHRA) and RECs, as required (may be delegated to NCTU)

NB:Sponsors of the International sites may delegate specific responsibilities e.g. Data management to Newcastle University as outlined in the relevant delegation agreements or equivalent

10.4.4 Trial Steering Committee (TSC)

A TSC will be convened. The TSC will consist of up to 5 independent members including as a minimum an independent chairperson, an independent clinician, an independent patient representative and the Chief Investigator. In addition, representatives of the Trial Management Group, country specific Sponsors and Funder will be invited to attend or dial in via teleconference as needed but will not be voting members. Membership, responsibilities and quoracy requirements will be defined in the MCDS-Therapy TSC Charter, which will be reviewed at the first TSC meeting. At the first meeting, the TSC will also decide on the frequency of meetings, this is anticipated to be every 6-12 months throughout the trial. The role of the TSC will be to monitor progress and supervise the trial to ensure it is conducted to high standards in accordance with the protocol, the principles of GCP, relevant regulations and guidelines. The TSC will advise on whether to continue or discontinue the trial and make a recommendation to Sponsors and Funder. If the trial is prematurely discontinued, participants will be informed, and no further trial data will be collected. The TSC will be overarching and will review conduct at each individually sponsored site.

10.4.5 Independent Data Monitoring Committee (IDMC)

An IDMC will be convened. The purpose of this committee will be to independently monitor safety and data and will consist of at least three independent members including one independent clinician and an independent statistician. At the first meeting, the IDMC will agree on its charter of operation, how many times the IDMC should meet over the course of the trial, and possible adoption of formal stopping rules for safety. Membership, responsibilities and quoracy requirements will be defined in the MCDS-Therapy IDMC Charter. The IDMC will be overarching and will monitor safety and data for each individually sponsored site.

10.4.6 Trial Management Group

A Trial Management Group (TMG) will be appointed and will be responsible for overseeing the dayto-day progress of the trial. The day-to-day management of the trial within the UK will be co-ordinated by Newcastle Clinical Trials Unit (NCTU). The NCTU may also be delegated specific tasks from the international site Sponsors. The Trial Management Group will include the CI, Senior Trial Manager, Trial Manager(s), Statistician, UK Sponsor Representative, Data Manager, Project Manager, Co-Investigator(s) and Pharmacist, as appropriate.

Quality control will be maintained through adherence to NCTU and UK Sponsor Standard Operating Procedures (SOPs) where applicable, the trial protocol, the principles of GCP, research governance framework and applicable clinical trial regulations.

In the UK, the following functions falling under the responsibility of the UK Sponsor will be delegated to the Chief Investigator and supported by NCTU:

- Reporting and notification to Medicines and Healthcare products Regulatory Agency (including obtaining clinical trial authorisation, notification of protocol amendments, submission of Development Safety Update Report (DSUR), notification of end of trial and submission of final trial report)
- Ethics Committee Opinion (including application for research ethics committee favourable opinion, notification of protocol amendments and end of trial, site specific assessment & local approval)
- HRA and Health and Care Research Wales (HCRW) Approval
- Adherence to Good Clinical Practice and Trial Conduct (including Good Clinical Practice (GCP) arrangements, data monitoring, emergency & safety procedures)

10.5 Notification of Deaths

All deaths will be reported as SAEs irrespective of the cause of death and reported to the Sponsor (NCTU should be notified) (see section 10.2).

10.6 Pregnancy Reporting

As the trial IMP CBZ (Tegretol[®]) is a known teratogen, the drug poses a significant risk to the foetus. The participants and their parent(s)/legal guardian(s) will be informed of the risks prior to taking part in the trial and will provide consent/assent to regular pregnancy testing and agreement to use contraception throughout the trial and for a period of 28 days after discontinuation of treatment (see section 8.3).

In the event of a UK trial participant becoming pregnant whilst receiving IMP, the participant must cease treatment immediately. The trial site must notify NCTU, the Chief Investigator and the UK Sponsor representative within 24 hours of becoming aware of the pregnancy.

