7 ELIGIBILITY CRITERIA

7.1 Inclusion Criteria

- Participants where a pathogenic mutation in the gene encoding the COL10A1 protein has been identified by sequence analysis
- Ambulant at the time of consent/assent, with open epiphyses
- Willing and able to attend for safety monitoring assessments
- Willing and able to adhere to the trial visit schedule and other protocol requirements

- Capable of giving informed consent, or if appropriate, have an acceptable individual capable of giving consent on the participant's behalf (e.g. parent or legal guardian of a child under 16 years of age)
- Written informed consent signed by parent(s)/legal guardian(s) and/or the subject, according to the local regulations
- If female and of childbearing potential, the participant must have a negative pregnancy test [urine beta-human chorionic gonadotropin (β-hCG)] at baseline and agree to regular pregnancy testing throughout the trial
- Sexually active female participants of childbearing potential must practice true abstinence in line with their preferred and usual lifestyle, or use two acceptable effective methods of contraception whilst on treatment and for a period of 28 days after discontinuation: a barrier method such as a condom or occlusive cap (diaphragm or cervical/vault cap) with spermicidal foam/gel/film/cream/suppository and an established non-barrier method such as oral, injected, or implanted hormonal methods (hormonal preparations must contain not less than 50µg oestrogen). Use of some alternative non-hormonal method of contraception should be considered: an intrauterine device or intrauterine system for the entire duration of the treatment period and for a period of 28 days after discontinuation.

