8.3 Pregnancy discussion

Due to the teratogenic nature of the trial drug, discussions regarding pregnancy will take place during the informed consent/assent process to ensure all potential female participants of child bearing age are aware of the risks of becoming pregnant whilst taking part in the trial. The trial team member taking consent/assent will discuss pregnancy with both the potential participant and their parent(s)/legal guardian(s). Due to the sensitive nature of this topic, the participant will have the

opportunity to speak with the clinician without the parent(s)/legal guardian(s) present. Both potential participants and their parent(s)/legal guardian(s) will be required to provide consent/assent confirming, where appropriate, which contraception will be used for the duration of the trial and for 28 days after discountination of treatment and participants will commit to regular pregnancy testing for the duration of the trial.

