8.9 Withdrawal Criteria

Participants have the right to withdraw from the trial at any time without having to give a reason. Investigator sites should try to ascertain the reason for withdrawal and document this reason on the eCRF within the trial MACRO database and in the participant's medical notes.

The Investigator may discontinue a participant from the trial at any time if the Investigator considers it necessary for any reason including:

- Pregnancy
- Participant withdrawal of consent/assent
- Investigator's discretion that it is in the best interest of the participant to withdraw
- An adverse event that requires discontinuation of the trial medication or renders the participant unable to continue in the trial
- If a participant experiences unacceptable toxicity (more than one DLT)

If a trial participant withdraws from the trial all data collected to the point of withdrawal will be retained. Consent/assent will have been sought to allow this.

It should be noted that participants may also be given the option to withdraw from treatment only, but continue with follow-up as per the protocol schedule. This will be explicitly documented in the participants medical notes and within the eCRF.

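### Pregnancy notification is triggered only by conception on study drug, while the protocol requires contraception for a further 28 days in which no test or contact is scheduled after a final visit

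*Protocol*

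**What the plan says.** Protocol 10.6 gives the reason for precaution: CBZ "is a known teratogen, the drug poses a significant risk to the foetus". Participants and parents therefore give "agreement to use contraception throughout the trial and for a period of 28 days after discontinuation of treatment". The contraception criterion in 7.1 has the same end point, "whilst on treatment and for a period of 28 days after discontinuation", and 8.3 repeats the 28 days.

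The action rule in 10.6 reads "In the event of a UK trial participant becoming pregnant whilst receiving IMP, the participant must cease treatment" immediately. It continues: "The trial site must notify NCTU, the Chief Investigator and the UK Sponsor representative within 24 hours of becoming aware of the pregnancy". Section 10.6.1 then describes consent to follow the pregnancy, for UK participants. Section 10.6.2 describes follow-up to the end of the pregnancy and for 12 months after a live birth.

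On testing, 8.3 says that "participants will commit to regular pregnancy testing for the duration of the trial". Section 8.7.4 ties the tests to the schedules of events. The last test is at Visit 2.5 in Stage 2 (Table 9). In Stage 1 it is at Visit 2.5, or at Visit 2.9 for those who enter the extension (Table 7). The SAP adds nothing on pregnancy follow-up or reporting.

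**The concern.** The protocol sets a post-treatment period for one hazard, fetal exposure, and then writes a reporting rule that stops short of it. If a participant conceives in those 28 days, nothing in 10.6 obliges the site to notify or to follow the pregnancy. If she was treated up to her last visit, no scheduled procedure would find it.

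A trial report could then state that no pregnancies occurred in the precaution period when in fact nobody looked. The protocol makes contraception alone a weak safeguard, because 9.5 warns that the drug can reduce or remove the effect of hormonal contraceptives.

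**Working it through.** No calculation in the plan bears on this point, so the check sets the passages side by side.

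1. **Length of the precaution period.** Sections 7.1, 8.3 and 10.6 agree on 28 days after discontinuation. The documents call this a contraception period. Reading it as the period in which the sponsor considers a conception potentially exposed is an inference from the teratogen statement in 10.6.

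2. **Notification trigger.** It requires that the participant becomes pregnant while receiving the drug. The sentence on the 24-hour notice speaks of the pregnancy, which refers back to that trigger. Days after the last dose on which a new conception meets it: 0 of 28.

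3. **Scheduled detection after the final visit.** Table 9 prescribes no drug at Visit 2.5, and Table 7 prescribes none at Visit 2.9. For those who complete treatment, the 28 days thus begin at about the final visit. Tables 4, 7 and 9 show no later visit, call or test. Scheduled tests in the period: 0. The 28-day extension in 8.3 attaches to contraception, not to testing.

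4. **Conceived on drug, found later.** This meets the trigger, and the 24 hours run from the site becoming aware. A test at the final visit can still be negative for a very recent conception, and no later contact follows.

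5. **Early stoppers.**
   - Those who stop treatment but stay in follow-up (8.9) keep the visit schedule and its pregnancy tests. A pregnancy could be found, but a new conception within their 28 days would still miss the trigger.
   - Those withdrawn for severe side effects are contacted again within 7 days (8.8.1). That leaves at least 28 − 7 = 21 days with nothing scheduled.

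6. **Fallback routes.** Under 10.2, adverse events and serious adverse events are collected to the end of trial participation. Later serious adverse reactions are reportable if an investigator learns of them, and a congenital anomaly could arrive that way. Neither route makes the pregnancy itself notifiable.

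7. **Non-UK sites.** Sections 10.3, 10.8 and 10.9 pair their UK rule with a sentence giving the duty to the country-specific Sponsor. Section 10.6 has no such sentence. Section 8.7.12 leaves the sharing of safety information from international sites to delegation agreements and does not mention pregnancy.

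**The case against.** The strongest reply is that this is a small mismatch in safety wording. The trial plans 40 children of both sexes, and those who may reach skeletal maturity before the end of the study should not be included (7.2). Few girls will be of childbearing potential. Pregnancies conceived on drug are reportable whenever they come to light, and participants who remain in follow-up are still tested. All of this stands and limits the size of the point. It does not close the gap for conceptions after the last dose.

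A reader might infer more than the documents support:

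- **That 8.9 and 10.6 conflict, one permissive and one mandatory.** Section 8.9 says "The Investigator may discontinue a participant from the trial at any time if the Investigator considers it necessary for any reason including" and lists pregnancy. Section 10.6 concerns ceasing treatment. These are different acts, and 8.9 itself allows a participant to stop treatment and stay in follow-up. The two can be read together.
- **That the five non-UK sites in Table 3 have no pregnancy rule apart from 8.9.** Sections 7.1, 8.3 and 8.7.4, the testing rows of Tables 8 and 9 and the first paragraph of 10.6 carry no UK limit. Non-UK notification may be set out in delegation agreements that are not part of these documents. The supportable statement is that this protocol is silent on notification there.
- **That the uncovered share of time measures the risk.** For Stage 2 one could write 28/(365 + 28) = 7.1%. That is a share of calendar days. It says nothing about expected pregnancies, because the documents give neither the number of girls at risk nor a pregnancy rate.

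**Conclusion.** The point holds in a limited form. The contraception period runs 28 days beyond discontinuation, and the notification trigger does not. A conception in those 28 days is outside the stated rule for every participant. For participants treated up to their last visit, it is also not looked for.

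Two assumptions are made: that discontinuation means the last dose, and that the last dose falls at about the final visit for those who complete treatment. The consequence is a possible under-count of exposed pregnancies. The efficacy estimates and the rest of the safety analysis are untouched. The change is worth making because it costs almost nothing and determines which pregnancies are reported and followed.

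**What to change.** Reconcile 10.6 with 7.1 and 8.3 as follows.

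1. Leave the treatment-cessation sentence in 10.6 unchanged. Its limit to participants receiving the drug is needed there, because someone already off treatment cannot be told to stop it.
2. Give notification a separate sentence: any pregnancy with estimated conception from the first dose until 28 days after the last dose is notified within 24 hours of the site becoming aware, and is followed under 10.6.1 and 10.6.2.
3. Add one sentence, on the pattern of 10.3, 10.8 and 10.9, stating whether the country-specific Sponsor or the delegation agreement governs pregnancy notification at non-UK sites.

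The cost is an amendment to wording; the notification form and follow-up procedure already exist.

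Whether to add a contact or a pregnancy test 28 days after the last dose is for the clinical team. For a last visit on 31 January 2024 it would fall on 28 February 2024. That needs an exception to the data-collection date in 8.12, but it precedes the 31 May 2024 date for the final report given in Appendix 2. If no contact is added, the report should say that pregnancies after the final visit were not actively sought.
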